# 9. Data Analysis/Statistical Methods

The detailed methodology for summary and statistical analyses of the data collected in this clinical trial will be documented in a statistical analysis plan (SAP) that will be maintained by the sponsor. The SAP may modify the plans outlined in the protocol where appropriate; however, any major modifications of the primary endpoint definitions and/or their analyses will also be reflected in a protocol amendment.

### 9.1 Analysis Data Sets

The primary analysis will be conducted on the Intent to Treatment (ITT) data set. The ITT data set will consist of all donations where randomization was completed and the apheresis procedure was started by "Begin Draw" on the NexSys® PCS device.

Sensitivity analysis may be conducted using a Modified *ITT* (MITT) data set and the per-protocol data set. The MITT data set will consist of all complete donations (see Section 6.1.2), as well as all donations associated with a significant hypotensive (vasovagal/hypovolemia) adverse event according to the plasma center adverse event reporting system, based on the IQPP definitions.

The per protocol data set will consist of all donations where the apheresis procedure was successfully completed collecting at least 90% of target plasma volume as well as all donations associated with a significant hypotensive (vasovagal/hypovolemia) adverse event according to the plasma center adverse event reporting system, based on the IQPP definitions.

### 9.2 Sample Size Considerations

The clinical trial will use an adaptive design allowing for sample size re-estimation based on observed number of donations and observed significant hypotensive (vasovagal/hypovolemia) adverse events according to the plasma center adverse event reporting system, based on the IQPP definitions. The target sample size is approximately 24,000 donations which are expected to be contributed by around 5,000 - 6,000 donors (on average four to five donations per donor). The sample size of the clinical trial may be reevaluated based on the number of donations and observed significant hypotensive (vasovagal/hypovolemia) adverse event according to the plasma center adverse event reporting system, based on the IQPP definitions. The sample size adaptation rules and detailed sample size considerations will be specified in the SAP.

#### 9.3 Randomization

Donors must meet all inclusion/exclusion criteria at the time of randomization. Donors will be randomized 1:1 to the experimental group or the control group. As repeat donations by the same donor are expected, the donor will remain in the same study group during the entire course of the clinical trial.

The randomization will target equal allocation of the number of donors in each group per site. Additionally, the randomization will be stratified by the donor's newcomer status (first-time donor vs. repeat donor) and the expected number of repeat donations. A block randomization procedure with variable block sizes will be used.

Allocation of subjects to clinical trial groups will proceed based on the block randomization procedure outlined above. Once subjects are enrolled, they will have been randomly assigned to the experimental or control group and the assignment information will be synchronized with the NexLynk® system. The randomization system will provide a confirmation report containing the subject number and the randomization code.

### 9.4 Analysis of Primary Endpoint

The primary analysis will be performed on the ITT population. The primary analysis will assess and compare the incidence rate of at least one significant hypotensive (vasovagal/hypovolemia) adverse event according to the plasma center adverse event reporting system, based on the IQPP definitions, across the two clinical trial groups. The analysis will be conducted using repeat measure logistic regression models. The primary endpoint, i.e., the significant hypotensive (vasovagal/hypovolemia) adverse event rates according to the plasma center adverse event reporting system, based on the IQPP definitions, will be compared across the two groups in the framework of non-inferiority hypothesis testing.

### 9.5 Secondary Analysis

Analysis of the secondary endpoints will be outlined in the SAP. Continuous and discrete modeling techniques will be used whenever applicable.

Effectiveness analysis will be conducted by comparing the distribution of collected plasma volumes across the two groups of the clinical trial.

The rates of AEs will be assessed relative to plasma volume, collection time, and the number of collection cycles. Assessment and comparison of the relative rates will be conducted using repeat measure models and descriptive statistical techniques. The secondary analysis – assessing time to adverse events – will be conducted using a survival analysis modeling framework and hazard estimation. Subgroup analysis will be based on descriptive statistical summaries. Descriptive statistical summaries and advanced data visualization techniques will be used for data presentation.

# 9.6 Exploratory Analysis

Exploratory analysis will be conducted as deemed appropriate. Continuous and discrete modeling techniques will be used whenever applicable. Distribution summaries will be presented by means of summary tables and visualization methods.

# 9.7 Interim Analysis

One or more interim analyses may be conducted. The interim analysis may result in the reassessment of the sample size or in early termination of the trial due to safety considerations. The sample size reassessment guidelines and statistical boundaries related to the primary endpoint will be outlined in the SAP.

# 9.8 Risk-Based Data Monitoring

Risk-based monitoring will be utilized for the trial based on a central statistical monitoring approach. Details will be outlined in the data monitoring plan. Key risk indicators may include, but are not limited to, device performance metrics, drop-out rates, assigned versus actual randomization, adverse event reporting, enrollment, subgroup imbalances, compliance to the protocol, and repeat donation frequencies. In the event where data monitoring indicates that a particular site, operator or machine is

not performing as expected, appropriate intervention may be made. Interventions may include but are not limited to, retraining, adjustment of the randomization scheme, site audits, enrollment suspension or site termination.

Safety monitoring on a real-time basis will be implemented, such that the sponsor, and independently the Principal Investigator, will be able to take appropriate steps to manage emergent safety signals, e.g., to put on hold or stop the clinical trial in case a safety signal is observed. In addition, an external Data Monitoring Committee will perform a review of the safety data for the interim analysis and will be making recommendations concerning the safe continuation of the clinical trial.

The sponsor will have real-time access to updates on adverse events occurring in the trial as reported by Octapharma Plasma (OPI). These will be reviewed by the medical/clinical experts in the sponsor organization on an on-going basis to monitor safety during the trial. The Principal Investigator will have access to the same information and will perform a review independently of the sponsor. Any significant hypotensive (vasovagal/hypovolemia) adverse events (primary endpoint) and Important Medical Safety Events (IMSEs), as well as confirmed or suspected MDR reportable events will trigger a notification to qualified sponsor personnel and to the Principal Investigator. Important Medical Safety Events have been defined by the sponsor's medical/clinical team, in alignment with the Principal Investigator, and are based on the OPI Medical Incidence Report (MIR) classification. These events are defined prior to the start of the trial (see Appendix 16.3) and will be used to identify acute important safety signals that may require urgent intervention by the sponsor.

The sponsor plans to hold regular weekly data review meetings, or more frequently if deemed necessary per event notifications described above. During these meetings the sponsor team will review new significant hypotensive (vasovagal/hypovolemia) adverse events (primary endpoint) and important medical safety events, as well as confirmed or suspected MDR reportable events to determine if any actions need to be taken. Further, an overview of adverse events grouped by the OPI Medical Incidence Report (MIR) classification will be reviewed to identify higher than expected frequencies of adverse events as compared with historic information (if available) or different distributions between the study arms.

OPI will continue MDR reporting and all MDR relevant events will be reported to the sponsor. Moreover, all MDR-relevant events will automatically be categorized as important medical safety events for the purpose of this study.

Safety signals will include: a) MDR reportable events in study subjects if they are unexpected, b) an accumulation of certain adverse events: (1) MDR reportable events, (2) important medical safety events, and (3) primary endpoint relevant events, if they occur beyond the expected rate (based on historical data, if available) or with a concerning statistically significant difference between the two study arms.

The sponsor will be informed of MDR reportable events within 24 hours.

Given the low anticipated frequency of adverse events, it will be nearly impossible to make statistically significant determinations about unusually frequent rates of events until late in the enrollment, unless the adverse event rate is dramatically increased. For this reason, unless there is a statistical determination by the study statistician, unusual safety signals will be independently reviewed by the Principal Investigator and sponsor (medical/clinical team) based on their medical/clinical expertise and experience. They will come to an independent assessment whether the event rate is unusual and whether the safety

signal requires further investigation. If necessary, the sponsor will request an ad hoc DMC meeting to solicit their feedback. The DMC will review adverse events during the 3-4 planned meetings during the course of the study, or during any of the before mentioned requested ad hoc meetings, and will provide independent advice.

Adverse events will be monitored in a real-time manner by the study statistician. Statistical summaries and model-based adverse event rate estimates will be used to present the current information on the adverse events by their categories (see three categories in section on safety signals above), and study arms (marked randomly as A and B). Study arm sample sizes, as well as 95% confidence intervals for adverse event rate estimates, will also be reported and visualized.

Whenever possible, the current AE rates will be compared with historic rates using metrics such as the likelihood of observing the current (or more extreme) AE rates under the relevant historic assumptions. If the observed rates are unexpectedly high (unlikely to observe under historic assumptions) notification indicating a safety signal will be generated and communicated to qualified sponsor personnel (medical/clinical team) and the Principal Investigator.

The adverse event rates will statistically be compared between the two study arms by testing the null hypothesis of equal AE rates (for the three above-defined AE categories). In the event that the between arm comparison suggests that the AE rates are significantly different, notifications indicating a safety signal will be generated and communicated to qualified sponsor personnel (medical/clinical team) and the Principal Investigator.

Upon identification of a safety signal the sponsor will fulfill its obligation to further investigate the safety signal and to appropriately respond to it. Remedial actions can include, but are not limited to, issuing queries, implementing operational changes to the conduct of the trial, retraining the sites, sending protocol deviation alert letters, amending the clinical trial protocol, requesting unblinding of the data for further analysis, etc.

Ultimately the sponsor may need to make a determination about the continuation of the study. Based on the available information, the sponsor (medical/clinical team) will decide to make modifications, to proceed without adjustments or to discontinue the study. The sponsor can reach out to the DMC to request an ad hoc meeting to review the safety signal and to provide an independent assessment to the sponsor. In line with the DMC charter the DMC may ask to review unblinded data as necessary to come to a reliable conclusion (this could allow the sponsor to stay blinded).

Safety signals will not automatically be raised to the DMC, with the exception of a death of a subject, which would be shared with the DMC within 24hrs of the sponsor's awareness of the event.

The Principal Investigator has access to the same information as the sponsor and will be informed of the sponsor's review and response to potential safety signals. The Principal Investigator will conduct an independent review of safety signals based on clinical experience and expertise and make an independent determination.

The sponsor will apply criteria by which to determine if it is safe to continue the study, such as the ones listed below.

- 1) Is the re-evaluated individual and collective risk profile outweighed by the benefits of the study?
- 2) Is it likely that a given adverse event may re-occur during the remainder of the study, and that its occurrence will likely carry unacceptable risks?
- 3) Does the statistical and medical/clinical analysis of the safety signal conclude that there is a correlation and likely causative relation with the study intervention?
- 4) Has the event happened in the intervention group (please note that the sponsor team should stay unblinded to the extent possible, while fulfilling its safety monitoring obligations and responsibilities)?

These criteria will be shared with the DMC, which will determine, based on these or alternative criteria that they may independently develop, the safety of continuing with the study.

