#### Or if there are:

• 2 or more severe hypotensive events [1.5 (Hypotensive; Severe (With or Without LOC)) or 1.6 (Hypotensive; Injury)] of the IQPP definition, as applied in the plasma center adverse event reporting system, at any point in the first 10,000 donations, reported to the sponsor,

the DMC will be informed within 24 hours and will perform an unblinded review. The DMC should make a determination by the end of the next business day after the event was reported to the sponsor.

If the DMC determines relatedness and decides that the safety profile of the study should be reconsidered, the study is put on hold immediately. Information of the event and DMC's decision is transmitted to FDA immediately. The study is not resumed unless and until FDA has decided that it is safe to do so.

If the DMC determines that the event is unrelated, or that the safety profile of the study remains unchanged, the study can be continued without interruption. In this case all information and the documentation of the DMC's decision is immediately brought to FDA's attention for further review at FDA's discretion.

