# 12.3 Data Monitoring Committee

This clinical trial will use an independent external Data Monitoring Committee (DMC). All voting members of the DMC will be external to Haemonetics. The DMC will meet regularly and will monitor the safety of the trial, according to the DMC charter.

The sponsor's criteria will be shared with the DMC, which will determine, based on these or alternative criteria that they may independently develop, the safety of continuing with the study. This evaluation will be based on a comprehensive review of the available safety information as the clinical trial progresses. The DMC may have access to additional information in its review, e.g., from a requested unblinded data review, that may allow them to come to a more informed decision. Their independent assessment will be shared with the sponsor team.

The DMC will also review data related to the stopping rules, as defined in section 9.10. The DMC will determine if it is safe to continue the trial or will decide to terminate the study. This decision is binding for the sponsor.

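### Protocol 9.8 is inconsistent on sponsor blinding and DMC notice, and a significant difference between arms has no automatic route to the DMC

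*Protocol*

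**What the plan says.** Four parts of the plan bear on who is told of a safety signal and who may know the arm.

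- **Comparison of arms (Protocol 9.8).** The study statistician monitors three event categories in real time by "testing the null hypothesis of equal AE rates (for the three above-defined AE categories". The categories are MDR reportable events, important medical safety events and primary-endpoint events. If the rates differ significantly, "notifications indicating a safety signal will be generated and communicated to qualified sponsor personnel (medical/clinical team) and the Principal Investigator". On the available information, "the sponsor (medical/clinical team) will decide to make modifications, to proceed without adjustments or to discontinue the study". The sponsor may ask the DMC for an ad hoc meeting.
- **DMC notice (Protocol 9.8).** "Safety signals will not automatically be raised to the DMC, with the exception of a death of a subject".
- **Stopping Rule 2 (Protocol 9.10, repeated in SAP 3.6).** The triggers are one or more severe hypotensive events (categories 1.5 or 1.6) in about 150 roll-in donations, or two or more in the first 10,000 donations. The action is that "the DMC will be informed within 24 hours and will perform an unblinded review".
- **Blinding.** The fourth example criterion for the sponsor in 9.8 reads "Has the event happened in the intervention group (please note that the sponsor team should stay unblinded to the extent possible". By contrast, the Synopsis (Clinical Trial Duration) wants the blinding of the sponsor's study team kept intact. Earlier in 9.8 the running summaries label the arms A and B at random, and unblinded review by the DMC is offered as a way to keep the sponsor blinded. Protocol 7 limits blinding to select members of the sponsor team, under a blinding plan that is not in the documents.

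**The concern.** A reader of 9.8 alone gets two wrong messages: that death is the only event sent to the DMC without a request, and that the sponsor team should be unblinded. The example criterion on the arm adds to the second, because summaries labelled A and B cannot answer it unless someone breaks the code. The text does not say who.

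Two things are at stake. The first is donor protection: the finding that most needs arm-level review, a significant excess in one arm, is not sent automatically to the independent committee. The second is the sponsor's blind. Sites know the arm, because Protocol 8.3 gives each group its own product code and device location, and donors may guess it. Important analysis choices also remain open. SAP 4 allows interim boundaries and decision rules to be settled as late as one week before interim unblinding. SAP 3.1.1 calls the correlation model still in progress, and SAP 3.2 defers detail on other secondary endpoints. Those choices are best made by people who do not know the arms.

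**Working it through.** The point rests mainly on comparing the text. The arithmetic only shows how much Stopping Rule 2 covers and what the fix might cost.

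**1. Blinding.** The instruction to stay unblinded is qualified by the sponsor's need to meet its safety monitoring obligations. That qualification makes sense only if the intended word is blinded, which also agrees with the A/B labels and the Synopsis. The word is probably a slip, but it stands in an operative safety procedure.

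**2. DMC notice.** Section 9.8 names one exception, death. Section 9.10 has two automatic notices, death and Stopping Rule 2. The list in 9.8 is therefore incomplete.

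**3. Does Stopping Rule 2 cover the between-arm signal?** Inputs:
- severe hypotensive rate 1/10,000 per donation (SAP 3.2)
- significant hypotensive rate 0.15% (Protocol 1.1, SAP 5)
- target of 24,000 donations (Protocol 9.2).

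I assume that severe in SAP 3.2 means categories 1.5 and 1.6, as in the stopping rule.

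- The plan's own figure first. SAP 3.2 puts the chance of at most 2 severe events in 12,000 procedures above 88%. The binomial gives P(X ≤ 2 | n = 12,000, p = 0.0001) = 0.8795, which agrees after rounding (it is just under 88%).
- Main trigger: P(X ≥ 2 | n = 10,000) = 1 − 0.9999^10,000 − 10,000 × 0.0001 × 0.9999^9,999 = 0.264.
- Roll-in trigger: P(X ≥ 1 | n = 150) = 1 − 0.9999^150 = 0.015.
- Donation window: 10,000 / 24,000 = 42%, leaving 14,000 donations outside it.
- Share of primary-endpoint events in its categories: 0.0001 / 0.0015 = 1/15, about 7%.

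Stopping Rule 2 is thus a real route: it has about a 26% chance of alerting the DMC at the historical rate. But it is a pooled count, not a comparison of arms. A difference driven by categories 1.2 to 1.4, or one arising after donation 10,000, does not trigger it.

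**4. What would automatic notice of between-arm differences cost?** Section 9.8 gives no significance level and no number of looks, so the load cannot be derived from the plan. As an illustration, assume weekly looks over 4 to 6 months (17 or 26 looks), an unadjusted two-sided 5% test, the primary-endpoint category only, independent donations and 0.15% in both arms. In 20,000 simulated trials of about 12,000 donations per arm, the chance of at least one false flag was:

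| Test | 17 looks | 26 looks |
|---|---|---|
| Exact conditional | 11.3% | 11.8% |
| Normal approximation | 21.3% | 23.4% |

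Testing all three categories, or looking more often, would raise these figures.

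**The case against.** The case on the other side has weight. The sponsor's criteria are introduced as examples, so the sponsor is not obliged to judge by arm. Requesting unblinding is a listed remedial action, and only select sponsor staff are blinded. The medical/clinical team may be an unblinded group under the blinding plan. The DMC reviews adverse events at its planned meetings, receives the sponsor's criteria, reviews safety data for the interim analysis and may see unblinded data. The Principal Investigator has the same information and judges independently. Section 9.10 presents its rules as additional to 9.8, which softens the conflict over death as sole exception. Events are classified at the plasma center with at least two internal reviews and physician confirmation (Protocol 5.1), so a sponsor that learns an arm does not thereby bias classification.

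All of this stands, and it rules out several stronger readings that a reader might infer:

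- **That the DMC is bypassed.** The text does not support this. What is missing is automatic notice between meetings.
- **That about 36 events (24,000 × 0.0015) pass through this route.** Those are expected individual notifications. A signal needs an accumulation beyond the expected rate or a significant arm difference.
- **That one event decodes the A/B labels.** This would need fixed labels and traceable single-event changes in the summaries, neither of which is stated.
- **That the DMC's advisory role contradicts its binding one.** In Protocol 12.3, "This decision is binding for the sponsor" directly follows the sentences on the stopping rules, so it can coexist with advice on other signals.

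The objection does not remove the wrong word, the incomplete list or the missing automatic route for a between-arm difference.

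**Conclusion.** The point holds in a limited form. Section 9.8 gives a blinding instruction opposite to the plan's evident intent, leaves open who answers the arm question, lists automatic DMC notices incompletely, and does not send significant between-arm differences to the DMC. On the SAP's rates, and on the assumption about severe made above, Stopping Rule 2 covers about 7% of primary-endpoint event types and 42% of planned donations, and compares no arms.

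The conclusion assumes that unblinded is a slip and that neither the blinding plan nor the DMC charter already settles these matters. If they do, 9.8 should say so. The documents do not show that the blind is broken or that the endpoint is biased. The change should be made; it does not call the design into question.

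**What to change.** Amend Protocol 9.8, and the DMC charter to match:

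1. Correct unblinded to blinded in the note to the fourth criterion, after checking it against the blinding plan.
2. State that the DMC, or a named unblinded person outside the study team as the blinding plan allows, answers whether the event was in the intervention group. The blinded team receives only the resulting decision.
3. Reconcile the sentence on automatic notice with 9.10 by listing Stopping Rule 2 events beside death, and add the statistician's significant between-arm differences, supplied to the DMC by actual arm. The stopping-rule thresholds need not change.

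Automatic DMC notice of every signal based on historical rates would go further. That is a governance choice, and this point does not require it.

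The cost is wording, with no added donors or procedures, plus some extra DMC notifications. Their number is unknown until the plan states a significance level and a schedule of looks for the running comparison; stating both would let it be estimated.
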